3.2.2 Selecting Individual Respondents for the IBBA

Sampling sub-populations of the type of interest for Avahan presents significant challenges. First, lists (or sampling frames) of sub-population members rarely if ever exist. Secondly, because they often represent a small proportion of the general population, obtaining statistically reliable data for such sub-populations through conventional household surveys would require prohibitively large household samples. Third, many of the types of dwellings in which they live (e.g. brothels, migrant hostels, prisons or unconventional dwellings) might not be included in typical household survey sampling frames. Finally, because they engage in behaviors that are illegal or at least stigmatized in many settings, members of such sub-populations are often reluctant to participate in household surveys and risk revealing their behaviors to others who may be present at the time of a survey.

In recent years, a number of sampling approaches have been developed for hard-to-reach and hidden populations that appear to produce survey estimates with acceptable levels of accuracy. Such methods will be used for the IBBA.

The choice of sampling method for individual sub-population members will depend upon the specific group being assessed. Two alternative sampling approaches will be used for the sub-groups included in the IBBA: time-location sampling and respondent driven sampling. (In a few rare situations, conventional cluster sampling will be used for some types of sex workers).

In time-location sampling (TLS), a sampling frame will be obtained through a listing exercise conducted by the IBBA research agency. The listing exercise will use existing information from all existing sources and add to it. From the geographical sites identified during mapping/listing, a time-location sampling frame consisting of venue/time slots will be constructed. Subsequently a random or systematic sample of primary sampling units, (i.e. venue/time slots) will be chosen and data on behavioral and biological indicators will be gathered from a random or systematic sample of population sub-group members appearing at those venues during fixed-length observation periods (e.g., three-hour time segments, entire days or nights). Examples of sites used in TLS for population sub-groups included in the IBBA are brothels, service bars (Mumbai only), street sites where sex workers congregate to solicit clients; and truck stops, border crossings, and bars/restaurants along major highways. Cluster sampling will be used for sex workers and truckers. The specific types of sites to be listed will be finalized after the pre-survey assessment. For MSM/MSW the sampling method will vary by state, and will depend on how the groups are defined in each state, which is related to the way the Avahan program defines and targets them. For clients of sex workers, field trials will help determine which sampling method works best. For IDUs it is proposed to use RDS.

In general RDS will be used for sub-populations for whom significant proportions do not congregate at identifiable sites. RDS is an elaboration of chain-referral sampling (CRS) designed to overcome the major biases associated with CRS methods such as snowball sampling. This is accomplished by, among other things: (1) restricting the number of recruits per recruiter and weighting the data inversely to personal network size to prevent the sample from being dominated by “seeds” and recruits with large personal networks; and (2) providing incentives to reduce non-response bias. We anticipate using this method for sampling IDUs and possibly other groups such as male sex workers or MSM.

3.3 Sample Sizes

3.3.1 *Measuring Changes in Behaviors and documenting STI Prevalence*

Sample sizes for each population sub-group included in the IBBA have been calculated on the basis of the following factors typically used in surveys with probability samples:

1. the expected baseline value of key behavioral indicators (e.g. consistent condom use with various partner types)
2. magnitude of change it is desired to be able to detect;
3. confidence level;
4. statistical power; and
5. design effect.

The following formula was used to determine the sample size for target groups for the IBBA:

$$n = D \frac{\left[\sqrt{2P(1-P)}Z_{1-a} + \sqrt{P_1(1-P_1) + P_2(1-P_2)}Z_{1-b} \right]^2}{\Delta^2}$$

Where:

D = design effect;

P_1 = the estimated proportion at the time of the first survey;

P_2 = the proportion at some future date, such that the quantity $(P_2 - P_1)$ is the size of the magnitude of change it is desired to be able to detect;

$$P = (P_1 + P_2) / 2;$$

$$Z_2 = (P_2 - P_1) / \sqrt{P(1-P)}$$

$Z_{1-\alpha}$ = the z-score corresponding to the probability with which it is desired to be able to conclude that an observed change of size $(P_2 - P_1)$ would not have occurred by chance;

$Z_{1-\beta}$ = the z-score corresponding to the degree of confidence with which it is desired to be certain of detecting a change of size $(P_2 - P_1)$ if one actually occurred.

For the IBBA, the following assumptions have been made regarding these parameters:

1. Expected baseline value: 50%. Measurements require the highest sample size to detect change when the baseline is 50%, hence this figure was used. If it can be safely assumed that baseline values of all indicators are significantly lower or higher, then sample sizes could be lowered.
2. Desired change to detect: 10-15%. This refers to the amount of change that can be detected between two survey rounds. For example, if condom use changed by an absolute 10-15%, this would be detected as a statistically significant change. A lower absolute change would not be detected as statistically significant. Smaller differences require larger sample sizes.
3. The alpha level has been set at 0.05, corresponding to 95% confidence in the observed estimates.
4. The beta level has been set at 0.10, corresponding to 90% power.
5. Design effect: 1.7 for time-location sampling and 1.5 for RDS. This adjusts for the use of sampling designs that are not simple random methods, e.g. cluster sampling.

Minimum sample size requirements per sub-population per district to measure both differences between groups and changes over time at the levels of significance and power indicated above are summarized in the table below. These numbers will be adjusted upward after the pilot test to account for anticipated non-response (refusal and duplication).

Justification for IBBA sample sizes for key sub-populations

IBBA Population	Indicator	Expected baseline value	Change to Detect	% in denominator	Design Effect	Required sample size	Sample size (rounded off) required for the IBBA
1. FSW Brothel based	Consistent condom use with clients	50%	15%	ALL	1.7 TLS	385	400
2. FSW Non-brothel based	Consistent condom use with clients	50%	15%	ALL	1.7 TLS	385	400
3. FSW Highway based	Consistent condom use with clients	50%	15%	ALL	1.7 TLS	385	400
4. Male Sex Worker/MSM	Consistent condom use with clients	50%	15%	ALL	1.5 RDS	339	400
5. Injecting Drug User	Consistent use of safe injecting equipment	50%	15%	ALL	1.5 RDS	339	400
6 Clients of FSW (Male bridge group)	Consistent condom use with FSW	50%	15%	ALL	1.7 TLS	385	400
7. Truckers	Consistent condom use with FSW	50%	15%	65%	1.7 TLS	592	600

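### The protocol says a 10-15 point change would be detected, but the per-district samples are sized for 15 points only; at the assumed 50% baseline a true 10-point change has 58-64% power

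*Protocol*

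**What the plan says.** Protocol section 3.3.1 lists five planning assumptions and then tabulates the sample sizes.

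- Baseline: "Expected baseline value: 50" percent, chosen as the value that needs the largest sample.
- Change: "Desired change to detect: 10-15" percent, described as the amount detectable between two survey rounds. The text continues: "For example, if condom use changed by an absolute 10-15%, this would be detected as a statistically significant change". It then adds: "A lower absolute change would not be detected as statistically significant".
- Error rates: "The alpha level has been set at 0.05, corresponding to 95% confidence in the observed estimates" and "The beta level has been set at 0.10, corresponding to 90% power".
- Design effect: 1.7 for time-location sampling (TLS) and 1.5 for respondent-driven sampling (RDS).

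The table is introduced as giving the "Minimum sample size requirements per sub-population per district to measure both differences between groups and changes over time", at the significance and power just listed. All seven rows have a 50% baseline and a 15% change. Required sizes are 385 (TLS groups), 339 (RDS groups) and 592 (truckers, 65% in the denominator). Planned sizes are 400, 400 and 600. No row covers a 10-point change.

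**The concern.** The text gives a range of detectable change, while the table is computed at one end of it. Required sample size rises roughly with the inverse square of the difference, so moving from 15 to 10 points more than doubles it. The lower end of the range therefore cannot share the 90% power claimed for the upper end.

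The stake is how district results will be read. If consistent condom use in a sub-population rose from 50% to 60%, the comparison of rounds would be non-significant in roughly 36% to 42% of cases. A reader told that such a change would be detected could take the result as evidence of no change.

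**Working it through.** **Inputs, all from Protocol section 3.3.1.** P1 = 0.50; alpha 0.05; power 0.90; D = 1.7 (TLS) or 1.5 (RDS); truckers' denominator 65%; equal numbers per round. The printed formula, with P the mean of P1 and P2, is

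n = D × [√(2P(1−P)) × z_alpha + √(P1(1−P1) + P2(1−P2)) × z_power]² / (P2 − P1)²

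The formula prints Z with subscript 1−a, but the table's figures require the two-sided z = 1.96. A one-sided z gives 313 and 276 in place of 385 and 339. I use 1.96 and 1.2816.

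**Step 1: reproduce the table (50% to 65%).**
- Bracket: 0.6991 × 1.96 + 0.6910 × 1.2816 = 1.3702 + 0.8856 = 2.2558.
- Before the design effect: 2.2558² / 0.15² = 226.16.
- TLS: 226.16 × 1.7 = 384.5 (table 385).
- RDS: 226.16 × 1.5 = 339.2 (table 339).
- Truckers: 384.5 / 0.65 = 591.5 (table 592).

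**Step 2: same formula at the lower end (50% to 60%).**
- Bracket: 0.7036 × 1.96 + 0.7000 × 1.2816 = 1.3790 + 0.8971 = 2.2760.
- Before the design effect: 2.2760² / 0.10² = 518.0.
- TLS: × 1.7 = 880.7, so 881.
- RDS: × 1.5 = 777.1, so 778.
- Truckers: 880.7 / 0.65 = 1,354.9, so 1,355.

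**Step 3: power at the planned samples.** Invert the formula with effective size m = (planned n in the denominator) / D:

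power = Φ{[(P2 − P1)√m − 1.96 × √(2P(1−P))] / √(P1(1−P1) + P2(1−P2))}

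For TLS, m = 400/1.7 = 235.3 and the argument is (0.10 × 15.34 − 1.379) / 0.700 = 0.221, so power is 0.588. The other groups follow in the same way; truckers have 600 × 0.65 = 390 in the denominator.

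| Group | m | Power, 50% to 60% | Power, 50% to 65% | Change with 90% power | Change with 80% power |
|---|---|---|---|---|---|
| TLS, n = 400 | 235.3 | 58.8% | 91.1% | 14.7 points | 12.8 points |
| RDS, n = 400 | 266.7 | 64.2% | 94.1% | 13.8 points | 12.0 points |
| Truckers, 390 of 600 | 229.4 | 57.7% | 90.4% | 14.9 points | 12.9 points |

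A fall from 50% to 40% gives the same figures by symmetry.

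**Step 4: the sentence ruling out smaller changes.** The smallest observed difference that reaches two-sided significance is 1.96 × √(2P(1−P)/m). With P = 0.55 this is 9.0 points (TLS), 8.4 (RDS) and 9.1 (truckers). An observed change of 9.5 points would be significant in every group, so the sentence is wrong for observed changes. For true changes it is also too absolute, since power does not drop to zero below the design value.

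**Step 5: sensitivity.** With a one-sided test, taking the printed subscript literally, power at 10 points becomes 70.5% (TLS), 75.2% (RDS) and 69.5% (truckers), still below 90%. Away from the 50% baseline, power for 10 points rises: from 70% to 80% it is 71%, 76% and 70%; from 80% to 90% it is 86%, 90% and 85%.

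**The case against.** The strongest defence is that the sentence speaks of an observed change. The protocol words its definition of the significance z-score in those terms: "the z-score corresponding to the probability with which it is desired to be able to conclude that an observed change of size". At the planned samples, an observed change of 10 to 15 points would indeed be significant. On that reading the sentence is true. It does not rescue the text. The item is the change to detect, an input to a formula whose power term concerns a change that really happened, and it stands beside a 90% power requirement. The observed-change reading also makes the very next sentence false, because observed changes below 10 points can be significant.

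A second defence is that the range is shorthand for different baselines: 15 points at 50%, fewer elsewhere. Part of this stands. The 58-64% power, and the miss rate of about 4 in 10, hold only near 50%; a reader might infer that any 10-point change is missed that often, and step 5 shows otherwise. But 50% is the stated assumption, no baseline condition is attached to the range, and power from 70% to 80% is still only 70-76%.

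Third, the table states 15% in every row, the text says that smaller differences need larger samples, and no sample size or procedure is affected. That is fair, and it limits the matter to a correction of wording. The planned increase after the pilot does not help at 10 points, because it is meant to offset refusal and duplication.

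**Conclusion.** Assumption 2 is wrong at its lower end. At the protocol's 50% baseline, with its design effects and a two-sided 0.05 test, the planned samples have 58-64% power for a true 10-point change, not 90%. The change detectable with 90% power is 14.7 points (TLS), 13.8 (RDS) and 14.9 (truckers). The sentence that excludes significance for smaller changes is also wrong.

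Three stronger conclusions might be inferred and are not supported:

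- The sample sizes are not miscalculated: they are correct for 15 points.
- Per-district behavioral change cannot be called the main behavioral outcome. The table is sized per district, but section 2.0 asks for trend data without ranking outcomes, and section 3.4.2.2 allows results to stand alone or be aggregated.
- Pooling districts cannot be offered as a ready route to 10 points. The protocol gives no pooled design effect, and section 3.2.1 describes districts chosen purposively to represent different socio-cultural regions.

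**What to change.** In section 3.3.1:

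1. Restate assumption 2 as 15 percentage points from a 50% baseline with 90% power, per sub-population per district (about 14 points for the RDS groups at n = 400; about 12-13 points with 80% power).
2. Add that power for a 10-point change from a 50% baseline is only 58-64%, and is higher at baselines far from 50%.
3. Delete the sentence saying that a smaller change would not be significant. If a threshold is wanted, say that observed changes of about 8.4-9.1 points or more reach significance near the 50% baseline.

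The cost is wording only. No respondents are added and the table stays as it is, but the stated detectable change becomes less favourable. If 10 points per district is truly required, the alternative is to size for it: 881, 778 and 1,355 per round, more than twice the tabulated requirements.

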3.3.2 Measuring Changes in HIV Incidence

Based on the BED Incidence EIA testing procedure, individuals tested are classified into three groups:

1. those who are HIV seronegative (N_{neg});
2. those who were infected within the last W days (i.e., 153 days) preceding the test (N_{inc}); and
3. those who were infected more than W days preceding the test ($N_{prevalent\ at\ day - W} = N_{tested} - N_{neg} - N_{inc}$).

For the analysis of incidence, one ignores those in category 3 above, since as they sero-converted longer in the past than the “window” period for the BED-CEIA, they are “non-informative” for the purpose of measuring HIV incidence. Thus, the number of ‘informative’ participants for the incidence analysis is N_{neg} plus N_{inc} .

The recommended approach for estimating the “incidence (density) rate” ($IDR_{per\ 100\ person-years}$) (i.e., events per 100 years of risk) and a 95% confidence interval for the incidence rate treats the number of recent infections as a Poisson random variable with total time at risk equal to the time at risk among the sero-negatives ($N_{neg} * 153$ days), plus average time at risk among the incident cases ($N_{inc} * 153$ days /2). An alternative measure for summarizing incidence is the “cumulative incidence” (P_t) which is the probability of becoming infected by the end of some time period t (e.g., $t=1$ year or $t=153$ days). When the risk of experiencing the event of interest during the exposure period of interest is constant (as is assumed when the Poisson model is applied as above) there is a convenient 1 to 1 relationship between P and IDR as shown below:

$$P_{t\ years} = 1 - \exp(-IDR_{t\ years}) \quad \text{or} \quad IDR_{t\ years} = -\ln(1 - P_{t\ years})$$

For example, if the $IDR_{1\ year} = .05$ events per person-year (or 5 events per 100 person-years) then the probability that a person who is followed for one year experiences the event within that year ($P_{1\ year}$) is .0488. Alternatively, if $IDR_{1\ year} = .05$ this implies that $IDR_{153\ days} = .02096$ and $P_{153\ days} = .02074$.

Using the BED-IEIA test results, we can estimate $P_{153\ days}$ directly for a cross-sectional sample using the observed proportion $N_{inc} / (N_{neg} + N_{inc})$. Thus, if our goal is to test whether two independent groups have the same risk of HIV incidence we can simply compare the observed proportions of participants with an infection within the past 153 days (among the informative participants) for the two groups using standard approaches for dichotomous variables (e.g., a chi-square test for a two by two table). Note that the two groups being compared can be samples from two separate populations, or two independent samples from a given population taken at two different points in time. The latter scenario would apply in the case of measuring changes in incidence over time for the sub-populations of interest for Avahan.

A sizeable number of calculations were run with different combinations of parameters, including underlying annual infection probabilities of between 1% and 25%. These

calculations reveal that on the order of 1,200 to 1,500 subjects per sub-population per round of IBBA would be needed to measure declines in incidence of five (5) percentage points. Thus, measuring changes in incidence for individual sub-populations within IBBA domains (i.e., districts) is not feasible, but is feasible for most groups when aggregate estimates at the state or overall Avahan project level are desired.

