3.1.3 Key behavioral and biological indicators

Behavioral Indicators

- Sexual risk behavior including number and type of sex partners ("commercial", "regular" and "non-regular")
- Condom use with different types of sex partners
- Other practices related to condom use and safe sex
- Knowledge of STIs and STI care-seeking behaviors
- Knowledge and attitudes toward HIV/AIDS
- Drug and substance use (including injecting and equipment sharing)
- Mobility and migration patterns influencing sexual behavior and risk
- Perception of HIV and STI risk
- Exposure to Avahan and other HIV/AIDS prevention interventions

Biological Indicators

- STI prevalence (syphilis serology, *N. gonorrhoeae* (Ng), *C. trachomatis* (Ct), herpes simplex virus (HSV) 2 serology, HBC and HCV in IDUs, and for those reporting ulcers *T. pallidum* (Tp), *H. ducreyi* (Hd) and HSV-2 antigen detection)
- HIV prevalence
- HIV incidence (BED-CEIA validated for Indian sub-type C)

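### The 95% interval for the HIV incidence level treats the 153-day BED window as exactly known, so it is too narrow, and more so as districts are pooled

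*Protocol*

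**What the plan says.** Protocol section 3.3.2 sorts tested people into HIV-negative (N_neg), recently infected (N_inc) and longer infected. The recent group is "those who were infected within the last W days (i.e., 153 days) preceding the test". The recommended estimate of the rate, with "a 95% confidence interval for the incidence rate", "treats the number of recent infections as a Poisson random variable". Time at risk is N_neg × 153 days, "plus average time at risk among the incident cases", which is N_inc × 153/2 days. The worked example converts a yearly rate to the window with the same fixed 153 days.

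Between-round change is handled differently, by comparing N_inc/(N_neg + N_inc) with "a chi-square test for a two by two table". The section finds that measuring changes is not possible by district but is "feasible for most groups when aggregate estimates at the state or overall Avahan project level are desired".

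On the assay, section 3.1.3 lists "HIV incidence (BED-CEIA validated for Indian sub-type C", and section 4.3 says much the same. Neither gives a standard error, interval or range for the window, and neither says where 153 days comes from. Section 10.1 lists incidence data as an output and says the data are critical to the models of infections averted.

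**The concern.** W is not a follow-up time set by design. It is the mean time that infected people stay in the assay's recent state, and it can only be learned from a finite sample, so it has sampling error. If W is 10% too long, every incidence level is about 10% too low, in every district and in the same direction.

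Poisson error falls as districts are added. Error in W does not, because it is one number applied to everyone. An interval that admits only the first source is nearly right for a single district and gets worse with aggregation.

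At stake is how precise the reported incidence levels appear, and how much confidence is placed in whatever the modelling partner builds on them. The problem is separate from clustering and remains after a design effect has been applied.

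**Working it through.** **1. The protocol's own figures (section 3.3.2).** With W fixed at 153 days:

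- 0.05 × 153/365 = 0.02096 (stated .02096)
- 1 − exp(−0.02096) = 0.02074 (stated .02074)
- 1 − exp(−0.05) = 0.0488 (stated .0488)

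All three reproduce, which confirms that W is used as an exact constant.

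**2. Where W enters.** With W in years, the rate is I = N_inc / [W × (N_neg + N_inc/2)]. So log I = log[N_inc/(N_neg + N_inc/2)] − log W. To first order,

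Var(log I) = D/N_inc + CV_W²,

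where D is the design effect and CV_W = SE(W)/W. The protocol's interval uses 1/N_inc only.

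**3. Inputs.**

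- Rate 5 per 100 person-years: the worked example.
- Prevalence 10%: assumed.
- CV_W of 5, 10 and 15%: assumed, since the protocol gives none.
- D = 1, as the interval is written, or 1.7, the time-location value in section 3.3.1.
- 1,500 tested: upper end of the size in section 3.3.2.
- 3,200 tested: 8 districts (section 3.2.1, the largest state) × 400 (section 3.3.1).
- 9,600 tested: 24 districts × 400, with 8 + 6 + 2 + 3 + 5 = 24 in the five states listed in section 3.1. This is an upper end for one sub-population.

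**4. Coverage of the nominal 95% interval.** Expected recents = tested × 0.90 × 0.02074. With s = √(D/recents), coverage = 2Φ(1.96·s/√(s² + CV_W²)) − 1.

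| Tested | Recents | D | s | CV 5% | CV 10% | CV 15% |
|---|---|---|---|---|---|---|
| 1,500 | 28.0 | 1 | 0.189 | 94.2% | 91.7% | 87.5% |
| 3,200 | 59.7 | 1 | 0.129 | 93.2% | 87.9% | 80.0% |
| 3,200 | 59.7 | 1.7 | 0.169 | 94.0% | 90.8% | 85.7% |
| 9,600 | 179.2 | 1.7 | 0.097 | 91.9% | 82.9% | 71.4% |

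Example at 3,200, D = 1, CV 10%: √(0.129² + 0.10²) = 0.164, so the interval should be 0.164/0.129 = 1.26 times as wide on the log scale. It goes from 3.88–6.44 to 3.63–6.89 per 100 person-years.

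**5. Change between rounds.** W does not enter the chi-square test. With window proportions 0.0207 and 0.0104, W = 120, 153 and 184 days all give a rate ratio of 2.00. The absolute difference does move: 3.18, 2.50 and 2.08 per 100 person-years.

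**6. Precision of an absolute decline at the planned size.** Take 1,500 tested per round, 10% prevalence, and a fall from 10 to 5 per 100 person-years. Recents are 55.4 and 28.0.

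- Poisson variance of the difference: 0.10²/55.4 + 0.05²/28.0 = 0.000270, so SE 0.0164.
- W adds (0.05 × CV_W)², which is 0.000025 at CV 10%, giving SE 0.0172, or 4.5% wider.
- Coverage is 94.7, 93.9 and 92.5% at CV 5, 10 and 15%. With D = 1.7 it is 94.8, 94.4 and 93.6%.

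**The case against.** The strongest reply is that section 3.3.2 is about measuring changes, and its planned test does not use W. That is correct. A reader might infer that the plan calls incidence levels usable at the pooled level, or that its conclusions on change are undermined. The text supports neither: the feasibility statement concerns changes, and the test of change and the ratio are untouched. What stands against the reply is that the same section also prescribes an interval for the level, and section 10.1 makes incidence data an output.

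Second, the size depends on a number the protocol does not give. At CV 5% and 1,500 tested, the interval should be only about 3% wider. This stands, and it is why a range is shown.

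Third, the lowest coverage figures need very large samples. One might infer that coverage falls to 60–75% in ordinary use. At D = 1, 9,600 tested would indeed give 75.9% at CV 10% and 61.8% at CV 15%. But that ignores the design effect and needs one sub-population to be sampled in all 24 districts, which no section states. Other states have 2 to 6 districts, or 800 to 2,400 tested. At 2,000 with D = 1.7, coverage is 94.4, 92.4 and 89.1%.

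Fourth, a reader might infer that 153 days and its standard error come from the sub-type C validation. The protocol says only that the assay was validated, so the source of W and the availability of a standard error are both open.

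Finally, modelling is done by a partner (section 2.0), and no section says that the interval, rather than the estimate, is passed on. The harm to the models is possible but not documented.

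**Conclusion.** The point holds for incidence levels. The protocol itself prescribes the interval, so this is not a detail left to a later analysis plan, and the interval omits an error that pooling cannot reduce. Size depends on the unknown CV of W. The effect is small at 5% with 1,200–1,500 tested. It becomes material at about 10% or more, or when several thousand are pooled: roughly 91% coverage at CV 10% for the largest state and 83% at the project-wide upper end, both with a design effect of 1.7. Absolute declines are affected only slightly at the planned size, and the between-round test and ratio not at all. The figures assume 5 per 100 person-years, 10% prevalence and a first-order log-scale approximation.

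**What to change.** In section 3.3.2:

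- State where the 153-day figure comes from and give its standard error.
- Compute the interval for incidence levels on the log scale, with variance equal to the design-based variance of log(N_inc/time at risk) plus [SE(W)/W]².
- If no standard error for W can be found, report incidence levels over a plausible range of W instead.
- Carry the same uncertainty into incidence levels supplied for modelling and into declines stated in percentage points per year.
- Leave the between-round chi-square test as it is.

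The change needs no further participants or specimens, only a documented source for W and one variance term or a sensitivity table. The cost is wider reported intervals for incidence levels. If tracing the source shows that W differs from 153 days, the point estimates would move as well.

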3.2 Site and Respondent Selection

3.2.1 Selecting Project Districts for Mapping, Size Estimation and IBBA

Presently Avahan is working in approximately 75 districts across six states of India, 19 districts in Andhra Pradesh, 20 in Karnataka, 16 in Maharashtra, 4 in Manipur, 4 in

Nagaland and 12 in Tamil Nadu. Based on the recommendation of a the WHO M&E Advisory Group for the IBBA, it was decided that the IBBA would be carried out in approximately 29 project districts, 8 in Andhra Pradesh, 5 in Karnataka, 6 in Maharashtra, 2 in Manipur, 3 in Nagaland and 5 in Tamil Nadu. In addition, five segments of the National Highway would also be part of the IBBA.

For selecting the IBBA districts within states, two key criteria were considered: (i) socio-cultural region (SCR); and (ii) size of the female sex worker (FSW) population, or, in the case of Manipur and Nagaland, size of the injecting drug user (IDU) population. Specifically, the requirement was to have representation from each of the different SCRs within a state to ensure heterogeneity in terms of social, economic and cultural characteristics. Then within each SCR the criterion was to select the districts with the highest number of persons at high risk (FSWs and IDUs). A third criterion, prevalence of antenatal clinic (ANC) attendees in the district was originally proposed to fulfill the objective of obtaining a mix of higher and lower prevalence districts. However, in the end, this criterion did not play a role because there were only a handful of cases where more than one district was selected within an SCR, and in those cases, after considering the size of the risk population, there was not much significant difference in terms of ANC prevalence. It is recognized that the size of the risk populations (FSW and IDUs) is fluid and that attempts to enumerate these populations at any given point in time will yield different results. However, since a probability-based method was not being used to select districts, the primary concern was to try to select the districts with the highest concentrations of at-risk populations. The proposed method adequately addresses this need.

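### The single figure of 1,200 to 1,500 subjects for a 5-point fall in HIV incidence cannot serve the stated 1-25% range, and the state-level feasibility drawn from it is unsupported for small states and for baselines above roughly 10%

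*Protocol*

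**What the plan says.** Protocol Section 3.3.2 plans to compare the proportion of recent infections (within a 153-day window) between rounds, using a chi-square test on a two-by-two table. The denominator is the HIV-negative plus the recently infected. Of people with long-standing infection it says "For the analysis of incidence, one ignores those in category 3 above".

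It then reports runs over many parameter combinations, including annual infection probabilities from 1% to 25%. The "calculations reveal that on the order of 1,200 to 1,500 subjects per sub-population per round of IBBA would be needed", and the target is stated as "would be needed to measure declines in incidence of five (5) percentage points". From this it concludes that incidence change cannot be measured by district, "but is feasible for most groups when aggregate estimates at the state or overall Avahan project level are desired".

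Section 3.3.1 sets the general design values. Section 3.3.2 does not say which of them, if any, entered the incidence runs.

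Section 3.2.1 gives the districts per state: 8 in Andhra Pradesh, 5 in Karnataka, 6 in Maharashtra, "2 in Manipur, 3 in Nagaland and 5 in Tamil Nadu". The table in Section 3.3.1 sets 400 respondents per group per district (600 for truckers).

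**The concern.** For a fixed absolute fall, the required number depends heavily on where incidence starts. It also depends on the design effect and on how many of those tested drop out of the denominator because of older infection. A single range with none of these inputs attached cannot be checked against a particular group or state, yet the protocol draws a design conclusion from it.

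HIV incidence is a listed biological indicator and a project output, in an assessment whose first objective is to measure impact. If a state-level comparison has far less power than readers assume, a null result could be taken for absence of effect. No rule in the protocol commits anyone to that reading, but the feasibility sentence invites it.

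**Working it through.** **Inputs.** "The alpha level has been set at 0.05, corresponding to 95% confidence in the observed estimates" and "The beta level has been set at 0.10, corresponding to 90% power" (Section 3.3.1). "Design effect: 1.7 for time-location sampling and 1.5 for RDS" (Section 3.3.1). Window 153 days, and two independent proportions with equal rounds (Section 3.3.2). HIV prevalence is not given, so any share excluded for older infection is an assumption.

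**Check of the formula.** For 50% against 65% and 90% power, the Section 3.3.1 formula with two-sided alpha gives 384.5 (D = 1.7), 339.2 (D = 1.5) and 591.5 (D = 1.7, 65% in the denominator). The table has 385, 339 and 592. So the protocol's alpha is two-sided in practice.

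**Conversion.** P153 = 1 - (1 - P_year)^(153/365). This gives 0.0432 for 10% and 0.0213 for 5%. The protocol's own example (0.0488 per year, 0.02074 per 153 days) also reproduces.

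**Worked case, 10% to 5%, D = 1, everyone informative.**
- Mean proportion 0.03224; difference 0.02193.
- n = [1.960 x sqrt(2 x 0.03224 x 0.96776) + 1.282 x sqrt(0.04133 + 0.02082)]^2 / 0.02193^2 = about 1,361.

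**Reproducing the stated range.** With D = 1 and no exclusions, 1,200 to 1,500 corresponds to baselines of about 9.1% to 10.8% (9%: 1,196; 11%: 1,521). It is not the only match at two-sided 0.05 and 90% power:
- D = 1.5, no exclusions: 6.8% to 7.8%.
- D = 1.7, no exclusions: 6.2% to 7.1%.
- D = 1.7, 20% excluded (assumed): 5.5% to 6.1%.

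**Required number per round, 90% power.** The last column is the number tested; the others are informative subjects.

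| Annual incidence | D = 1 | D = 1.5 | D = 1.7 | D = 1.7, 20% excluded (assumed) |
|---|---|---|---|---|
| 6% to 1% | 672 | 1,008 | 1,142 | 1,427 |
| 10% to 5% | 1,361 | 2,041 | 2,314 | 2,892 |
| 15% to 10% | 2,109 | 3,164 | 3,586 | 4,483 |
| 20% to 15% | 2,735 | 4,102 | 4,649 | 5,812 |
| 25% to 20% | 3,240 | 4,860 | 5,508 | 6,885 |

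Just above a 5% baseline the D = 1 need is about 490, so over the baselines where a 5-point fall is possible it varies more than six-fold (3,240 / 490 = 6.6).

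**Power at state totals.** The total is 400 x districts, assuming the group is surveyed in every district of the state. Power = Phi{[sqrt(n) x difference - 1.960 x sqrt(2P(1-P))] / sqrt(P1(1-P1) + P2(1-P2))}, with n = total x informative fraction / D.

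| State (total) | 10% to 5%, D = 1.5 | 10% to 5%, D = 1.7 | 10% to 5%, D = 1.7, 20% excluded (assumed) | 15% to 10%, D = 1.7 |
|---|---|---|---|---|
| Manipur (800) | 53% | 48% | 40% | 33% |
| Nagaland (1,200) | 70% | 65% | 55% | 47% |
| Tamil Nadu, Karnataka (2,000 each) | 89% | 85% | 77% | 68% |
| Maharashtra (2,400) | 94% | 91% | 84% | 76% |
| Andhra Pradesh (3,200) | 98% | 97% | 93% | 86% |

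With D = 1.7 and no exclusions, the highest baseline at which a 5-point fall has 90% power is 6.1% at 1,200, 8.8% at 2,000, 10.3% at 2,400 and 13.3% at 3,200. At 800 no baseline above 5% reaches it. All 29 districts (29 x 400 = 11,600) give about 99% or more at every baseline checked from 6% to 25%, even with D = 1.7 and 20% excluded.

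**The case against.** The figure is an order-of-magnitude note. The study is sized on behavioural change, and the section already rules out district-level incidence comparisons. The 1-25% describes the runs made, not a promise that one range fits every baseline, and values under 5% may have been end-points (6% to 1%, for example). All of that is fair.

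A reader might infer that the authors forgot the design effect and the loss of long-standing infections, because the D = 1 match near 10% is close. The protocol does not support that. It names no baseline, and the figure also fits baselines of about 5.5% to 7.8% with the stated design effects. Other power levels widen the choice: two-sided at 80% power, D = 1 fits 11.6% to 14.2% and D = 1.7 fits 7.6% to 8.9%. Omission is possible but not shown.

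What the objection does not remove is that a fall from 5.5-7.8% is a relative fall of 64% to 91% (5/7.8 and 5/5.5). That is a narrow part of 1-25% which the text never singles out. Manipur's 2 x 400 = 800 also falls below the protocol's own minimum without any re-analysis.

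**Conclusion.** The statement is wrong as written: one range is offered where the need runs from about 490 to 3,240 before any adjustment, and the state-level conclusion rests on it. At 90% power that conclusion is unsupported for Manipur at any baseline with D = 1.7, and for Nagaland above about 6%. For the other states it is unsupported above about 9% (five districts), 10% (Maharashtra) and 13% (Andhra Pradesh), with D = 1.7 and nobody excluded. Excluding older infections lowers these limits; D = 1.5 raises them somewhat.

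It would be too much to infer that state-level feasibility fails altogether. The two largest states reach 90% at 10% to 5% with D = 1.7 and no exclusions. The protocol's sentence also covers the overall project level, which holds if the group is surveyed in all 29 districts.

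The results assume two-sided 0.05, 90% power, 400 analysable respondents per district and coverage of every district in the state. The 10% and 15% baselines and the 20% exclusion are illustrations, not protocol values.

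**What to change.** In Section 3.3.2, replace the single range with a short table of required numbers by baseline incidence. Show design effects 1.5 and 1.7 and a range of informative fractions, and state the alpha and power used. Add the power at each state total (400 x number of districts). Limit the state-level feasibility sentence to the combinations that reach the stated power, and direct the smaller states to pooled estimates. Say that a 5-point fall is not a defined target where baseline incidence is 5% or less.

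The cost is a recalculation and a few lines of text. The feasibility statement becomes less favourable; no respondents are added and the behavioural sample sizes are untouched.
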